# 6. Study objectives

#### 6.1. Primary objectives

- 1. To assess the level of the first bilirubin measurement in neonates of different skin tones.
- 2. To assess the relationship between transcutaneous bilirubin (TcB) and serum bilirubin measurements (SBR) in neonates of different skin tones.

#### 6.2. Secondary objectives

- 1. To investigate immediate management of neonates of different skin tones undergoing assessment for jaundice; primarily length of admission and need for interventions including phototherapy and exchange transfusion.
- 2. To review the range of existing local guidelines relating to the management of neonates with jaundice, how these guidelines vary from each other and from

- national clinical practice guidelines (such as NICE Jaundice in newborn babies under 28 days Clinical guideline [CG98]) and the extent to which they are being adhered to.
- 3. To collate opinions and experiences from a diverse population of parents and carers regarding their understanding of jaundice in neonates and its management, the impact of skin tone and/or ethnicity on jaundice assessment in neonates and the acceptability of the neonatal skin tone tool.

## 6.3. Primary endpoints

- Absolute value of first bilirubin measurement in neonates of different skin tones
- 2. Value of first bilirubin measurement relative to NICE phototherapy / exchange transfusion treatment lines in neonates of different skin tones
- 3. Age of neonates of different skin tones at first bilirubin measurement
- 4. Indication for bilirubin assessment in neonates of different skin tones

[Assessed through data collected by local teams during prospective data collection]

### 6.4. Secondary endpoints

- 1. Diagnostic methods used to assess jaundice in neonates of different skin tones
- 2. Immediate management of neonates following jaundice assessment

[Assessed through data collected by local teams during prospective data collection]

3. Number of clinical practice guidelines used and variance between guidelines

[Assessed through data collected in pre-study survey of local leads at each site]

- 4. Acceptability of a validated neonatal skin tone tool in a diverse population of parents and carers
- 5. Parent and carer understanding of neonatal jaundice
- 6. Parent and carer opinions and experiences of the impact of skin tone and/or ethnicity on jaundice assessment in neonates

[Assessed through data collected in parents/carer completed surveys and through focus groups and semi-structured interviews]

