# 2. Qualitative data collection: parent survey and focus groups / semi-structured interviews

Qualitative data collection tools will include a parent / carer survey and focus groups and/or semi-structured interviews to collate opinions and experiences around the assessment and management of neonatal jaundice. Themes around the impact of neonates' natural skin tone and / or ethnicity on jaundice assessment and the acceptability of different methods of assessment will be explored and compiled.

These tools will be optional extra sections of the study which will be signposted to, both verbally and written within the parent information sheet, at the point of enrollment into the qualitative data section. Links within the PIS will take parents to a secure web-based survey platform containing an electronic consent form for this survey. Separate links will provide the additional option to sign up to parent focus groups or semi-structured interviews, with a separate electronic consent form for recording of sessions.

The survey will include multiple choice and free text guestions (See Table 2).

Focus groups will include 4-6 consenting participants and will run on approximately 2 occasions. Senior study leads will guide appropriate content for discussion and parent representative leads will help to facilitate groups.

Semi-structured interviews will run for 30-45 minutes and be recorded after consent. Senior study leads will guide appropriate content for discussion and parent representative leads will help in the inclusion of particular themes.

Themes addressed will include: Understanding of jaundice and experiences of assessment; Interactions between natural skin colour / race / ethnicity and the assessment of jaundice; Opinions on current jaundice guidelines (from local to international); Empowering parents: Parental education on jaundice, its detection and the deteriorating infant (in view of the RHO report recommendation); Opinions on changing practice.

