**Table 2: Datapoints collected for Secondary Objective 3** 

Datapoint	Source	Collection timepoint
Parent and carer survey	•	•
Eligibility confirmation	Microsoft Forms consent	Time of survey completion
Participant identifier	Microsoft Forms	Time of survey completion
Section 1: Experience of Jaundice detection and the Impa	act of Skin Tone	•
What do you understand by the term "newborn jaundice"?a	Survey	Time of survey completion
How would you rate your experience of having your baby assessed for jaundice? c	Survey	Time of survey completion
What led you to give that rating? a	Survey	Time of survey completion
Was there anything that concerned you about how your baby was tested, treated or how you were kept informed, or not? b	Survey	Time of survey completion
(If yes) Please tell us more about your answer.a	Survey	Time of survey completion
Have you had any other experiences of newborn jaundice? a	Survey	Time of survey completion
(If yes) Tell us briefly about this.a	Survey	Time of survey completion
Was there anything that concerned you about how the baby was tested, treated or how you were kept informed, or not? b	Survey	Time of survey completion
(If yes) Tell us briefly about this.a	Survey	Time of survey completion
Section 2: Perception of care and communication		·
Were you given any information or guidance by healthcare professionals on how to look for signs of jaundice in your baby? b	Survey	Time of survey completion
(If yes) What type of information or guidance did you receive? b	Survey	Time of survey completion
(If yes) Did this include an explanation of how your baby's natural skin tone might affect signs of jaundice?b	Survey	Time of survey completion
(If yes) Did this include pictures of jaundice in a baby that matched your baby's natural skin tone? b	Survey	Time of survey completion

(If yes) Do you feel confident in looking for signs of jaundice in your baby after receiving this information?	Survey	Time of survey completion
Whom would you first approach for advice if you were concerned your baby might have jaundice? b	Survey	Time of survey completion
How and when would you approach a healthcare provider to check your newborn baby for jaundice? a	Survey	Time of survey completion
Section 3: Recommendations		

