What are your views on how health professionals currently identify jaundice? Are there any aspects you think could be improved? a		
What is one thing you would like healthcare professionals to understand better about identifying jaundice in babies with different skin tones? a		
Section 4: Demographic information		
Self-identified ethnicity of participant b	Survey	Time of survey completion
How many children (including this baby) have you had?b	Survey	Time of survey completion
a Freetext answer. b Multiple choice answer. c Likert scale.		

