# Study procedure:

- The neonate's skin colour will be assessed as per the Neomar neonatal skin colour scale and categorised into one of four groups. We recognise that babies may be naturally lighter or darker than those depicted in the skin tone tool groups. When this is the case, babies will be assigned to the group closest to their natural skin colour e.g. for a baby who has a skin colour darker than group 4, they will be included within group 4.
- Additional data will be collected at two timepoints: enrollment and 14-days
- A full list of data collected including the data source and timepoints can be found in Table 1.
- Parents will be given the option to complete a web-based survey about their understanding of jaundice in neonates and its management and the impact of skin tone and/or ethnicity on jaundice assessment in neonates.

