# Appendix 3: focus group and semi-structured interview frameworks

## **Instruction for facilitators:**

The themes and questions below are guides for the discussion. Participants may wish to take the conversation in a different direction, but please ensure that you cover all of the themes listed.

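### Acceptability of the skin tone tool is a secondary endpoint, but no listed survey item, theme or interview prompt asks about the tool

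*Protocol*

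**What the plan says.** Secondary Objective 3 (synopsis and Section 6.2) has three limbs: parents' understanding of jaundice and its management, the effect of skin tone or ethnicity on jaundice assessment, and "the acceptability of the neonatal skin tone tool". Section 6.4 turns the third limb into endpoint 4, "Acceptability of a validated neonatal skin tone tool in a diverse population of parents and carers", and gives one source for endpoints 4 to 6: "Assessed through data collected in parents/carer completed surveys and through focus groups and semi-structured interviews".

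The content of those sources is set out in four places:

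- Table 2, captioned "Datapoints collected for Secondary Objective 3", gives the survey questions.
- Section 8, under qualitative data collection, lists the discussion themes, beginning "Themes addressed will include: Understanding of jaundice and experiences of assessment; Interactions between natural skin colour / race / ethnicity and the assessment of jaundice" and continuing with guidelines, parental education and changing practice.
- Appendix 3 gives the focus group and interview frameworks, and tells facilitators: "please ensure that you cover all of the themes listed".
- Section 9, under Study procedure, describes the survey: "Parents will be given the option to complete a web-based survey about their understanding of jaundice in neonates and its management". That sentence goes on to the impact of skin tone or ethnicity on assessment and stops there.

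**The concern.** An endpoint can be reported only if something collects it. Here the objective, the endpoint and the source are all stated, but the third limb of the objective drops out when the instruments are written.

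The matter is not incidental to this study. Skin tone as graded by the tool is the exposure for both primary objectives, and Section 8 says the grading is the only data taken from examining the baby. Section 5.3 treats parents' reaction to the tool as the main foreseeable risk, and Section 11 says much the same. In the public involvement work, two parents were uncomfortable because the darkest group might not represent the darkest babies (Appendix 1), and the parents' focus group raised what to do when a parent disagrees with the assigned category. The authors therefore expect the tool to draw comment, yet no listed question puts it to parents whose babies were graded.

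This is not a detail left to an analysis plan. Table 2 and Appendix 3 are the data collection instruments, and no analysis can supply answers to a question that was not asked. Survey responses are collected anonymously (Section 8, Data Entry Methods), so going back to respondents later would be difficult.

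**Working it through.** The plan states no figure here, so there is none to reproduce. The check is to read each instrument against the endpoint.

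**Survey (Table 2).** Leaving aside the eligibility and identifier rows, the questions number 9 in Section 1, 7 in Section 2, 2 in Section 3 and 2 in Section 4: 9 + 7 + 2 + 2 = 20.

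- Section 1: understanding of jaundice, a rating of the jaundice assessment with the reason, concerns about testing, treatment or information, and the same for any other experience of jaundice.
- Section 2: guidance received, whether it dealt with the baby's natural skin tone, whether pictures matched it, confidence, and whom to approach and when.
- Section 3: views on how jaundice is identified now, and one thing professionals should understand better about detecting it across skin tones.
- Section 4: "Self-identified ethnicity of participant" and number of children.

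Questions about the tool or the grading of the baby: 0 of 20. The nearest are the two skin tone questions in Section 2 and the last question in Section 3. All three concern jaundice and its signs.

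**Themes (Section 8).** There are five: understanding and experience, skin colour or ethnicity and jaundice assessment, guidelines, parental education, changing practice. Themes on the tool: 0 of 5.

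**Frameworks (Appendix 3).** Both use the same five themes. The prompts under the skin colour theme ask about concerns over how the baby was tested or treated, how parents were kept informed, and what contributed. Prompts on the tool: none in either framework.

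**Survey description (Section 9).** It covers the first two limbs of Secondary Objective 3 and omits the third.

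**Where the tool was asked about.** Appendix 1 reports 32 responses to the pre-study survey, with 94% neutral, comfortable or very comfortable and 2 uncomfortable: (32 − 2)/32 = 93.75%, which agrees. Section 12 describes that question as how parents would feel about a tool being used, so it was hypothetical. The pre-study focus group of 5 parents also discussed the tool. Both came before recruitment, and neither is the source that Section 6.4 names. By contrast, Section 10.1 expects about 560 parents to be offered the study's qualitative parts.

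**The case against.** The strongest reply is that the instruments are more open than a count of questions suggests. Section 8 says the qualitative tools will explore how acceptable different methods of assessment are. Its theme list is introduced in words that do not close it, and parent representatives help to bring in particular themes. Appendix 3 calls its themes and questions guides and lets participants take the discussion elsewhere. Survey free text on concerns about testing could draw a comment on the tool. The feedback link in the information sheet is another route: Section 5.3 offers it for negative experiences with research staff, and Section 12 also opens it to ideas on study methodology.

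Much of this stands. A reader might infer that endpoint 4 will have no data whatever; the documents do not support that, because stray comments could arise by any of these routes. What does not follow is that the endpoint is measured. The Section 8 line is most naturally read as concerning methods of assessing jaundice, which the skin colour scale is not, and no question carries it forward. The feedback form is not a named source for endpoint 4.

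A reader might also infer that endpoint 6, on skin tone or ethnicity and jaundice assessment, is equally uncovered. It is not: both frameworks give it a theme, and the survey has questions on skin tone. Nor does endpoint 4 require survey answers to be tabulated by the baby's tone group, since the protocol promises only a diverse population of parents and records their ethnicity.

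**Conclusion.** The point holds, confined to endpoint 4 and the matching clause of Secondary Objective 3. The protocol promises a measure of the tool's acceptability and names the instruments, and those instruments contain no planned question on it: 0 of 20 survey questions, 0 of 5 listed themes, and no prompt in either framework. Run as written, the study could report only unprompted remarks or fall back on 32 hypothetical pre-study responses and one small focus group.

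This assumes that Table 2 and Appendix 3 show the full content of the instruments, as they appear to. If the live survey or a facilitator's guide already has a tool question, the protocol needs only to be brought into line.

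The consequence is limited. This is one limb of a descriptive secondary objective; neither primary objective, the sample size nor participant safety is affected. It is still worth correcting before the survey opens, because the repair is small then and difficult later.

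**What to change.** Add to Table 2 one item on how acceptable the parent found the use of the skin tone tool on their baby, followed by free text. The comfort question from the pre-study survey can be reused, reworded to ask about actual use. Include a response for tool not used or opted out, because Section 7.1 admits parents who declined the quantitative part. Add a matching prompt to the Section 8 theme list and to both Appendix 3 frameworks, and mention the tool in the Section 9 description of the survey.

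If the team prefers not to ask, delete endpoint 4 from Section 6.4 and the acceptability clause of Secondary Objective 3 from the synopsis and Section 6.2.

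The cost is a minor amendment, re-translation of the new text and a slightly longer survey. Parents need not be told the assigned tone group. That would add a sensitive step, given the distress risk in Section 5.3 and the response plan for parents who disagree with the category, which was still to be developed after the parents' focus group. Endpoint 4 does not need it.

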#### 5. Introduction

# 5.1. Background

Jaundice is one of the most common conditions affecting newborns in the first weeks of life. The consequences of delayed recognition and treatment of jaundice can be devastating; kernicterus is an avoidable condition that causes lifelong neurodisability if hyperbilirubinaemia is not promptly treated. A 2020 UK-based study found that infants from Black, South Asian or other ethnic groups were at a disproportionate risk of developing this complication, making up 50% of all cases of kernicterus despite representing only 25% of live births. Another study based in the UK and Ireland in 2007 found an association between ethnic minority origin and severe hyperbilirubinaemia.

The recent NHS Race and Health Observatory review of neonatal assessment and practice in Black, Asian and minority ethnic newborns highlights the potential for bias in the assessment of jaundice in neonates with darker skin tones . It recommends several areas for further research, including a better understanding on the level at which jaundice is visible, particularly in darker skinned neonates, and further investigation into the level at which a transcutaneous bilirubinometer (TcB) reading should be followed up by a serum bilirubin (SBR). The report also highlights that ethnicity does not correlate well with neonatal skin tone .

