#### **Data Entry Methods**

Skin tone and clinical data collected from each participant will be recorded via a Case Report Form (CRF) and stored in a secure database (REDCap). Responses from the parent survey will be collected anonymously onto the secure NHS Microsoft 365 Forms web-based platform, which has routinely been used in other studies. Parent focus group and interview data will be recorded and transcriptions will be securely stored for data extraction to create a narrative summary.

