## **Appendix 1: Summary of PPI scoping survey**

We received 32 responses from parents or carers with experience of postnatal care based within the London region. Many parents / carers understood newborn jaundice to be about "yellowing of the skin" and "elevated bilirubin". Parents mentioned yellowing of the eyes and problems with the liver as well as a need for it to be treated. Most parents (88%, n= 28/32) had experienced an infant they were caring for, being checked for or diagnosed with jaundice. There was a wide variation of self-identified ethnicity within this group, with 10 distinct ethnic groups as per the standardised NHS categories, and some choosing "any other". When asked whether they felt the baby's natural skin tone or ethnic background had any impact on this assessment, roughly a third said yes, a third said no and the remaining third wasn't sure (36%, 36% and 28% respectively). Themes they raised around this included:

- Feeling healthcare professionals had repeated misplaced concerns about their baby being jaundiced because of mixed race ethnicity;
- Jaundice investigations and treatments not being consented for or explained adequately.
- Baby's changing natural skin tone in the first days of life, affecting the ease in identifying jaundice.
- Paler babies appeared more jaundiced than they were, so investigated more.
- Difficulties identifying jaundice in some ethnicities over others.

When asked about how parents and healthcare professionals assess babies for jaundice, themes included:

- Many parents are aware that yellowing of the skin and eyes is a sign checked by both parents and HCPs.
- Others did not know how to identify jaundice and there were calls for better explanations and advice for parents on discharge and better trained community staff.
- There were some calls for universal jaundice screening.
- Concerns that the race of the parents or the baby may influence HCP management.
- Concerns over racial microaggressions from HCPs when describing jaundice in mixed race skin tones.

Most parents / carers said they would feel either neutral, comfortable or very comfortable with a healthcare professional using our skin tone / colour tool (94%). 2 parents were uncomfortable with it as they were concerned that the darkest skin tone group would not account for babies with the darkest natural skin tones, therefore missing an important group.

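### The parent survey is named as a source for parents' experiences of how skin tone or ethnicity affected jaundice assessment, but none of its 20 questions asks about that effect directly

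*Protocol*

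**What the plan says.** Section 6.4 lists, as secondary endpoint 6, "Parent and carer opinions and experiences of the impact of skin tone and/or ethnicity on jaundice assessment in neonates". The note beneath endpoints 4 to 6 gives the sources: "Assessed through data collected in parents/carer completed surveys and through focus groups and semi-structured interviews". Section 9 (Study procedure) describes the instrument offered to parents as a "web-based survey about their understanding of jaundice in neonates and its management and the impact of skin tone and/or ethnicity on jaundice assessment". The first section of Table 2 is titled as covering both the experience of jaundice detection and the impact of skin tone.

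The questions in that first section are general. They cover what the parent understands by jaundice, a rating of the experience and the reason for it, other experiences of jaundice, and concerns, for example "Was there anything that concerned you about how your baby was tested, treated or how you were kept informed, or not". The demographic section holds "Self-identified ethnicity of participant" and the number of children.

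Appendix 1 reports that the pre-study scoping survey asked parents whether they felt the baby's "natural skin tone or ethnic background had any impact on this assessment", and gives the split as 36% yes, 36% no and 28% unsure. Section 5.2 cites this kind of response as part of the rationale for the study.

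**The concern.** The protocol gives the survey a purpose that its listed questions do not serve directly. A parent who believes that skin tone or ethnicity changed how the baby was assessed can say so only by raising it in answer to a general question. A parent who saw no such effect has nowhere to say that. Silence in the free text then has two meanings, that there was no effect or that the parent did not think to mention it, and the analysis cannot tell them apart.

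The survey is the qualitative instrument offered most widely, and the topic is the central theme of the study. If the direct question is missing, the experience part of endpoint 6 leans on the few parents who join a group or an interview. Because Table 2 is part of the protocol, this is not a detail left to a later analysis plan.

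**Working it through.** No formula applies. The check sets each question in Table 2 against endpoint 6 and then looks at the other source.

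**1. Count of survey questions (Table 2)**

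| Section | Questions | Mention skin tone | Ask whether tone or ethnicity affected the assessment |
|---|---|---|---|
| 1. Experience and impact of skin tone | 9 | 0 | 0 |
| 2. Perception of care and communication | 7 | 2 | 0 |
| 3. Recommendations | 2 | 1 | 0 |
| 4. Demographic information | 2 | 0 | 0 |
| Total | 9 + 7 + 2 + 2 = 20 | 3 | 0 |

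**2. The three items that mention tone.** The two in Section 2 are shown only to parents who were given information. They ask whether it explained how tone might alter the signs of jaundice and whether its pictures matched the baby. They concern materials, not the assessment. The item in Section 3 asks for one thing professionals should understand better about identifying jaundice across skin tones. That elicits an opinion, so it contributes to the opinion half of endpoint 6 but does not ask what happened to this baby.

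**3. The single item on ethnicity.** It records the parent's ethnicity as a demographic variable. It does not ask about any effect.

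**4. The groups and interviews (section 8 and Appendix 3).** The second theme in both frameworks is explicitly about skin colour, race and ethnicity in jaundice assessment, and the introduction tells participants that race and ethnicity are the subject. The theme has three numbered questions. Two ask about concerns in general terms, one on testing and one on treatment and information. The third asks what else contributed, with examples that include the professional's perceived ethnicity, institutional racism and microaggressions. None asks directly about the baby's own skin tone.

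**5. Reach of each source.** Section 8 plans about 2 focus groups of 4 to 6 parents, so 2 × 4 = 8 to 2 × 6 = 12 participants. The number of interviews is not stated. Section 10.1 expects at least about 560 parents to be offered the qualitative parts. That is a count of invitations, not of respondents.

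**6. Evidence that the question can be answered.** In the scoping survey 36% + 36% = 72% gave a definite yes or no and 28% were unsure. There were 32 responses in all, and the base for these percentages is not given. They show only that parents can answer and that answers differ.

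**The case against.** The strongest reply is that endpoint 6 is qualitative. It concerns opinions and experiences, it is shared between two sources, and no proportion is planned. Section 10.2 specifies thematic analysis of free text and transcripts, with an inductive approach that lets themes arise from the data. Open, non-leading questions suit that method. The Section 3 item does draw out opinions on tone, and the group and interview theme carries race-related prompts. Appendix 3 also tells facilitators that the questions are guides and that every theme must be covered.

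Much of this stands. A reader might infer that the survey cannot measure endpoint 6 at all, or that Appendix 3 asks nothing about race or ethnicity. The documents support neither reading. Nor do they show that the direct question was removed from the study survey. The scoping survey was a separate instrument for developing the protocol, and section 5.2 says its results helped to form the group and interview themes. The most that can be said is that the question was not carried over into Table 2.

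The reply does not remove the mismatch. Section 9 states what the survey is about, Section 1 of Table 2 is titled for it, and no question in that section names it. Open items can be kept first, so a direct item after them need not lead them.

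A reader might also infer that the survey fails because it records no infant skin tone. Section 5.1 does report that "ethnicity does not correlate well with neonatal skin tone", so parental ethnicity is a weak stand-in, and no link to the tone record is described: section 8 says "Responses from the parent survey will be collected anonymously". Table 2 lists a participant identifier, but section 9 (Participant withdrawal) describes only initials and a date, kept so that data can be removed. Endpoint 6, however, is not defined by tone group. It can be collected without infant tone, so this absence is a limit on description and not a defect in the endpoint.

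**Conclusion.** The point holds in a limited form. Endpoint 6 and the stated purpose of the survey include the impact of skin tone and ethnicity on the assessment, and 0 of 20 listed questions ask about it directly. The survey serves part of the opinion component. The experience component rests on unprompted free text and on a small group and interview sample, where the theme is explicit but the numbered questions do not ask about the baby's own tone.

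The consequence is under-recording of such experiences, and silence that cannot be interpreted. The size of the under-recording cannot be calculated from the protocol. The conclusion assumes that Table 2 is the complete survey. The endpoint is secondary and descriptive, and no primary result depends on it. The change is still worth making before data collection, because it is cheap and the loss cannot be repaired at analysis.

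**What to change.** Add to Section 1 of Table 2 an item based on the scoping-survey question in Appendix 1: whether the parent felt that the baby's natural skin tone or ethnic background had any impact on the assessment, answered yes, no or not sure, followed by free text. Place it after the open experience and concern items so that it does not lead them. Add the same direct prompt to the second theme of the focus group and interview frameworks in Appendix 3.

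The cost is one extra survey item with its free-text follow-up, one prompt in each framework and a minor amendment.

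Describing responses by infant tone is optional. It would need a consented link to the tone group assigned by the study team, which would end the stated anonymity and would be unavailable for parents who opted out of the quantitative part. Asking parents to choose the tone group themselves is a poor substitute: the parent focus group summary reports agreement that the team should assign it for consistency, and some parents were unsure of their baby's natural tone because of jaundice.
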